2.2 Abemaciclib (LY2835219)

Abemaciclib (LY2835219) is a selective and potent small molecule CDK4/6 dual inhibitor that is hypothesized to arrest tumor growth through prevention of cell cycle progression through the G1 restriction point. In humans, one study has been completed (I3Y-MC-JPBD [JPBD]) and 13 studies are ongoing including I3Y-MC-JPBA, I3Y-MC-JPBB, I3Y-JE- JPBC, I3Y-MC-JPBE, I3Y-MC-JPBH, I3Y-MC-JPBJ, and I3Y-MC-JPBN.

Absorption, Distribution, Metabolism, and Excretion

Abemaciclib (LY2835219) demonstrates moderate to high bioavailability in preclinical species. In humans, the terminal elimination half-life ($t_{1/2}$) in plasma ranges from approximately 17 to 38 hours across the dose range tested. At a single dose of 200 mg, the mean apparent oral clearance is 38.3 L/h with high inter-individual variability (105% coefficient of variation [CV]) and the apparent volume of distribution is large at 1300 L (96% CV). Following oral administration, abemaciclib was extensively metabolized followed by biliary excretion of metabolites.

Based on Study JPBD and in vitro data, CYP3A is responsible for abemaciclib metabolism, the primary route of clearance. Strong CYP3A inhibitors may increase abemaciclib exposures, and strong inducers may decrease abemaciclib exposures. Abemaciclib and its major metabolites did not substantially inhibit CYP enzymes in human liver microsomes; however, there was downregulation of mRNA for CYP1A2, CYP2B6, CYP2C8, CYP2C9, CYP2D6, and CYP3A. Caution should be exercised when coadministering abemaciclib with narrow therapeutic drugs that are substrates for CYP1A2, CYP2B6, CYP2C8, CYP2C9, CYP2D6, or CYP3A.

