8.1.8 Administration

O Abemaciclib will be administered at a starting dose of 150 mg every 12 hours. If a patient has not required dose reduction(s) due to toxicity, then the dose of Abemaciclib may be escalated at the start of Cycle 2 to 200 mg every 12 hours if the investigator determines that it is in the best interest of the patient. Doses should be spaced approximately 12 hours apart, with a minimum of 6 hours between doses. Abemaciclib should be taken with or without food at approximately the same times each day with a glass of water. Participants should be instructed to take their doses, twice a day, at approximately the same times each day and approximately 12 apart (for Cohort 1 pre-surgery abemaciclib should be taken as close to a 7AM – 7PM schedule as possible), except on the days of the pharmacokinetic sampling at which time the participant should be instructed to not take their morning abemaciclib dose until after their clinic visit. For Cohort 1 pre-surgery abemaciclib, the last dose should be on the day of surgery 1-3 hours prior to surgery and tumor removal. Since participants in Cohort 1 are undergoing PK testing, accurately recording the time of study drug

- administration on day of surgery and recording the time of tumor removal is especially important.
- o If vomiting occurs during the course of treatment, no re-dosing of the participant is allowed before the next scheduled dose. The occurrence and frequency of any vomiting during a treatment cycle must be recorded as an adverse event.
- o If the participant forgets to take his/her abemaciclib dose more than 6 hours from the participant's normally scheduled dosing time (i.e., less than 6 hours to the time of the next planned dose), then that dose should be withheld and abemaciclib should be restarted at the time of the next planned dose.

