Ten Green top tubes (each 10ml/tube – sodium heparin tubes preferred) should be collected prior to the start of pre-surgery Day 1 (pre-dose) and prior to morning abemaciclib dose on day of surgery. Blood samples for immunologic assays should be shipped (along with the fresh-preserved tumor tissue) via FedEX for overnight delivery directly to UCLA as described in Table 9.2.

Cohorts 1 & 2 Plasma Pharmacokinetic (PK) Samples:

Cohort 1 Pre-Surgery/Surgery

4mL blood should be collected in purple-top EDTA vacutainer (Becton Dickinson Catalog # 367861 or 367844, Franklin Lakes, NJ) prior to start of pre-surgery Day 1 (pre-dose), pre-surgery Day 8 (pre-dose), and on day of surgery at time of tumor resection. All samples should be prior to morning abemaciclib dose.

Cohort 2

For all Cohort 2 participants, 4mL blood should be collected (in purple-top EDTA vacutainer (Becton Dickinson Catalog # 367861 or 367844, Franklin Lakes, NJ) at C1D1 (pre-treatment), C2D1, C3D1 and C4D1(if a participant comes off study treatment prior to C4D1 visit, then an end of treatment sample should be drawn). All samples should be prior to morning abemaciclib dose.

Handling of Specimen(s)

- Obtain venous blood by standard phlebotomy technique from a peripheral access point. NOTE: Suggest using a minimum 18G needle to avoid sample hemolysis.
- Fill-up the tubes as much as possible until blood flow stops.
- GENTLY invert each tube several times (8-10 times) immediately after collection to avoid sample hemolysis.
- Place samples immediately **on ice** after collection; samples must be processed **within 20 minutes**.

Processing instructions

- 1. Invert sample 8-10 times immediately before processing.
- 2. Place the sample(s) on ice or in a refrigerator and separate the **plasma within 60** minutes of collection at 1,500 2,000 x g for 10 minutes in swinging bucket (SW) or 15 minutes in a fixed angel (FA) rotor at 4°C in a refrigerated centrifuge. Make sure that the centrifuge reaches speed and is maintained throughout the entire spin.
- 3. Carefully remove tube from centrifuge.
- 4. Using a pipette, transfer equal aliquots of plasma into 2 labeled 2 mL cryovials, not exceeding 1.5 mL per cryovial.
- 5. Label samples as Abemaciclib PK, including protocol number (16-383), unique patient ID (assigned by the consortium), initials, date of collection, draw time, and time point.
- 6. Store plasma samples at -70°C or below until shipment or transfer to OSU.

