- e. End of treatment assessments to be performed within +/- 7 days of last study drug or within +/- 7 days of decision to end treatment. All participants will be followed until resolution or stabilization of any serious adverse events occurring during treatment or starting within 30 days of last study drug.
- f. A contact/visit for review of concomitant medications, adverse events, and KPS (no neurologic exam required at 30-day FU time point) is to be performed at 30 days +7 days after the last study drug is given. This may be performed via documented phone conversation with a study nurse or clinician. All participants will be followed until resolution or stabilization of any serious adverse events occurring during treatment or starting within 30 days of last study drug.
- g. Participants will be followed via medical record review until death for post-treatment therapies, progression information, and survival. Updates to the CRFs are to be made roughly every three months (+/- 1 month). Each site will be responsible for collecting information on their participants regarding all post-treatment therapies, start and stop dates of those therapies, the reason for stopping those therapies, and the date of death.
- h. Per DF/HCC multi-center policy, must be obtained by MD attending. Informed Consent may be performed up to 28 days prior to registration.

- i. Please see section 3. Genomic profiling data from previously performed sequencing and/or copy number array data to verify status of CDKN2A/B/C and RB1 must be available prior to registration.
- j. Serum pregnancy test only for women of child bearing potential (as defined in Section 3.1.20). Serum pregnancy test within 7 days prior to Day 1 drug for registration purposes and repeated within 72 hours prior to Day 1 drug if original screening pregnancy test is not within 72 hours of Day 1 drug.
- k. Vital signs: Weight, heart rate, blood pressure, respiration rate, temp. Height required only at baseline (any height within 1 year of registration is acceptable).
- I. Karnofsky Performance Status (KPS)

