- m. Adverse events experienced by participants will be collected and reported from initiation of study medication, throughout the study, and within 30 days of the last dose of study medication. Participants who experience an ongoing adverse event related to a study procedure and/or study medication beyond 30 days will continue to be contacted by a member of the study team until the event is resolved, stabilized, or determined to be irreversible by the participating investigator. Concomitant medications and reason for administration should be documented in the case history from date of consent up to the 30-Day Post Drug Visit.
- n. EKG at screening and C2D1 only.
- o. Imaging: gadolinium-enhanced contrast and non-contrast MRI. CT alternative, if MRI contraindicated. When feasible at a site, appendix G MRI Acquisition Protocol should be adhered to and the same imaging technique should be used in a participant throughout the trial. Imaging to be done at all odd cycles (C3D1, C5D1, etc.).
- p. Within 14 days prior to registration (screening baseline scan). For the scan prior to treatment cycle 1 day 1, if steroids are added or increased between the date of the scan and the start of treatment, new baseline imaging is required.
- q. Response assessment using RANO criteria, at time of imaging and as indicated clinically.
- r. Hematology erythrocytes (RBC), hemoglobin, hematocrit, platelets, total WBC plus differential (neutrophils, lymphocytes, monocytes, eosinophils, basophils).
- s. Biochemistry albumin, alkaline phosphatase (ALP), bicarbonate (HCO₃), BUN, calcium, chloride, creatinine, glucose, magnesium, phosphorous, potassium, SGOT (AST), SGPT (ALT), sodium, total protein, total bilirubin, amylase and lipase, LDH and uric acid. If total bilirubin is greater than the upper limit of normal, direct and indirect bilirubin should be performed.
- t. Archival tumor tissue per eligibility point 3.1.11 must be submitted to the DFCI Coordinating Center within 60 days of registration Archival tumor tissue per eligibility point 3.1.11 must be submitted to the DFCI Coordinating Center within 60 days of registration.
- u. Required at C1D1 (pre-dose), C2D1, C3D1 and C4D1 for Cohort 2 participants. If a participant comes off study treatment prior to C4D1 then an end of treatment PK sample should be drawn. See section 9 for details on PK timing and processing requirements.
- v. Please see protocol section 8.1.8 for abemaciclib administration instructions.

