13.4 Analysis of Secondary and Exploratory Endpoints

Response rate will be the proportion of participants with measurable disease who experience complete or partial radiographic response determined by the RANO Criteria (Wen et al., 2010). Progression free survival, PFS6, and overall survival will be calculated using standard statistical methods. Safety will be summarized using descriptive statistics. Participants in Cohort 2 will not be replaced for any reason. If a subject enrolled in Cohort 1 is found at the time of on-treatment re-resection to have only necrosis and not recurrent disease, then s/he may remain on treatment but should be replaced for evaluation of endpoints.

In Cohort 1 & 2 plasma, and Cohort 1 tumor tissue levels of abemaciclib will be determined by liquid chromatography coupled with tandem mass spectrometry. Descriptive details of steady-state trough plasma levels, CSF and tumor tissue concentrations and tumor tissue to plasma ratios will be provided.

Other pharmacodynamic studies including immunohistochemistry and quantitative IHC analysis will be performed as in Section 9.0. Effects of abemaciclib on tumor cell proliferation and tumor cell death will be measured using immunohistochemistry for pRB1, Ki-67 and Cleaved Caspase 3. In general the pharmacodynamic and neuro-imaging results will be summarized in a descriptive manner with comparison between pre- and post-treatment assay results when possible.

Beyond the assessment of "success", more detailed analyses of the biological correlate data are exploratory. The statistical analysis will depend on the amount and quality of the data obtained as well as the overall success of the treatment.

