APPENDIX F ABEMACICLIB DOSING INSTRUCTIONS & DRUG DIARY (Cohort 1 Pre-Surgery)

o be completed by study personnel:							
Patient ID #	_ Patient Initials:	Pre-Surgery Cycle Month & Year:	Abemaciclib Dose:	_mg, two times a day.			
	TAKE	pill(s) in the morning and	_ pill(s) in the evening.				

Abemaciclib Description:

• Your study drug (Abemaciclib) is supplied as 50 mg mixture beige tablet.

Abemaciclib Instructions - When and How:

- Take study drug (Abemaciclib) twice a day, once in the morning and once in the evening.
- Take the drugs at approximately the same time each morning and evening, so that you are taking the drugs 12 hours apart. Morning and evening doses should be taken as close to a 7AM & 7PM schedule as possible (7 in the morning, 7 at night, 7 the next morning, and so on).
- Take the pill(s) with a glass of water and swallow them whole; do not chew them or crush them. Abemaciclib can be taken with or without food.
- Do not skip any doses.
- If you forget to take your pills in the morning you can take your missed dose up to 6 hours after your normally scheduled time. If it has been more than 6 hours, skip the dose and take the next scheduled dose at the usual time in the evening (one dose only). Please call your study nurse or doctor to discuss missed doses.
- If you forget to take your pills in the evening, you can take your missed dose up to 6 hours after your normally scheduled time. If it has been more than 6 hours from the missed dose (i.e., less than 6 hours to your next scheduled dose), skip the dose and take the next scheduled dose at the next usual time (one dose only). Please call your study nurse or doctor to discuss missed doses.
- If you vomit your pills, write this down in your pill diary. Do not take a replacement dose. Take the next scheduled dose as usual (one dose only). Please call your study nurse or doctor to discuss vomited doses.
- On the day of surgery, you will be asked to take your morning dose at the hospital; therefore, please bring your pills with you. Do not take any further doses after surgery. Return any remaining pills to the study team.

Additional Instructions:

- You must avoid eating or drinking any foods with Seville oranges (like marmalade), grapefruit or foods or drink with grapefruit, and any exotic fruits during the entire treatment period.
- You should drink 8 to 10 glasses of clear liquids a day for the entire treatment period.

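### The Cohort 1 diary omits the hold-dose instruction for the Day 8 PK sample, and Section 13.4 has no rule keeping off-drug end-of-treatment samples out of the Cohort 2 trough summary

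*Combined protocol and SAP*

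**What the plan says.** **Cohort 1.** Section 9.2, Table 9.2 and Table 10.1 footnote r all label the pre-surgery Day 8 plasma sample as pre-dose. Section 8.1.8 gives the near-7AM/7PM schedule and, in the same sentence, its exception: on PK sampling days "the participant should be instructed to not take their morning abemaciclib dose until after their clinic visit". Section 5.1 sends the reader to the diaries in Appendices E and F for instructions. Appendix F, the pre-surgery diary, carries the schedule ("Morning and evening doses should be taken as close to a 7AM & 7PM schedule as possible") and a special instruction for the day of surgery, but nothing for Day 8. Appendix E, the other diary, does tell patients to wait until after the visit at the start of cycles 2, 3 and 4.

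**Cohort 2.** PK samples are due at C1D1, C2D1, C3D1 and C4D1, all before the morning dose. For early stoppers, Section 9.2 adds: "if a participant comes off study treatment prior to C4D1 visit, then an end of treatment sample should be drawn". Table 10.2 footnote u repeats the rule: "If a participant comes off study treatment prior to C4D1 then an end of treatment PK sample should be drawn". No separate time limit is given for this draw. The only end-of-treatment window is footnote e: "End of treatment assessments to be performed within +/- 7 days of last study drug or within +/- 7 days of decision to end treatment".

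**Analysis.** Section 13.4 promises descriptive details of steady-state "trough plasma levels, CSF and tumor tissue concentrations and tumor tissue to plasma ratios will be provided". It does not define a trough by time since last dose, says nothing about end-of-treatment samples and does not group by dose. Section 2.2 states that the terminal half-life "in plasma ranges from approximately 17 to 38 hours across the dose range tested".

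**The concern.** A trough summary is interpretable only if each value was taken at the end of a dosing interval during continuous dosing. The plan leaves this open in two places, which differ in cause, direction and size.

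In Cohort 1 the patient-facing document and the protocol body disagree. A patient who takes the Day 8 dose near 7AM and then attends clinic gives a post-dose sample under a pre-dose label, which biases the trough upward. This cohort remained open when the protocol was last amended, so the gap can still affect data.

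In Cohort 2 an end-of-treatment sample can be a washout value, and the pre-dose condition has no meaning once dosing has ended. If such samples were pooled, the trough would be biased downward and its spread inflated. Section 1.1 gives the purpose of the limited PK work as checking that exposure in GBM does not differ from that in other solid tumors, so a spuriously low value would bear on that comparison.

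**Working it through.** The plan states no figure to reproduce here. The inputs are:

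- Half-life 17 to 38 h, apparent clearance 38.3 L/h and apparent volume 1300 L (Section 2.2). These agree with each other: ln 2 × 1300 / 38.3 = 23.5 h, inside the stated range.
- Dosing interval 12 h (Section 5.1).
- End-of-treatment window (Table 10.2 footnote e) and permitted delay of up to 28 days (Section 6.2.6).
- Assumption: one-compartment, linear kinetics.

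**Cohort 1, Day 8**

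1. Is Day 8 a sensible trough time? The fraction of steady state after 7 days is 1 − 2^(−168/t½): 99.9% at 17 h and 95% at 38 h. Yes.
2. How far could a post-dose sample overstate trough? With instantaneous absorption, the steady-state peak-to-trough ratio is 2^(12/t½): 2^(12/17) = 1.63 and 2^(12/38) = 1.24. The overstatement is therefore at most about 63% or 24%. Slower absorption makes it smaller, but the documents give no absorption rate, so only the bound is used.

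**Cohort 2, end of treatment**

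1. Relative to a 12-hour trough, a sample d days after the last dose holds 2^(−(24d − 12)/t½). At 7 days this is 2^(−156/17) = 0.0017 and 2^(−156/38) = 0.058.

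| Days since last dose | t½ 17 h | t½ 38 h |
|---|---|---|
| 1 | 61% | 80% |
| 3 | 8.7% | 33% |
| 5 | 1.2% | 14% |
| 7 | 0.17% | 5.8% |

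2. Seven days is not the outer limit. The window may be anchored on the decision to stop, so a 28-day hold followed by a draw 7 days after that decision is 28 + 7 = 35 days from the last dose, when essentially no drug remains.
3. It is not the typical case either. The window runs both ways, so a draw can also fall while the participant is still dosing.
4. What if such samples were pooled? With a share f of 7-day samples, each holding a fraction r of trough, the arithmetic mean becomes (1 − f) + f·r of the true trough. The share is an assumption, since the documents give no count: f = 10% gives 90% to 91%, 25% gives 75% to 76%, and 50% gives 50% to 53%.

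**Dose.** Section 5.1 allows a rise from 150 mg to 200 mg at Cycle 2, and Table 6.0 lists reductions to 100 mg and 50 mg. Under linear kinetics, 150 mg and 200 mg alone differ in trough by a factor of 200/150 = 1.33, so an ungrouped summary mixes exposures.

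**The case against.** The strongest reply is that nothing in the plan assigns end-of-treatment samples to the trough summary. The words steady-state trough argue against including them, just as nobody would include the C1D1 pre-treatment sample. Tubes carry draw time and time point, and the diary records dose times, so an analyst can separate them. Section 6.2.9 already tells sites to ask whether a sample falling within a drug hold is worth collecting, and it arguably reaches an end-of-treatment draw that follows a hold. All of this stands. It turns the Cohort 2 matter into a missing handling rule rather than an error, but without a stated rule the exclusion is left to judgement after the data are seen.

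A reader might also infer from the median PFS of 55 days (95% CI 49 to 56; Section 2.4), set against C4D1 on day 3 × 28 + 1 = 85, that at least half of the 32 participants contributed washout samples. The documents do not support that. The figure suggests how many came under the end-of-treatment rule, with PFS as a proxy for leaving treatment. It does not say how long after the last dose they were sampled. PFS runs from first dose, so 49 to 56 days correspond to study days 50 to 57. C3D1 is day 57, and its scan is due in the 7 days before. Many early stoppers may therefore have been identified at or near a scheduled PK visit, where a draw before that morning's dose would be a valid trough if drug had not already been stopped.

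On Cohort 1, it can be said that Day 8 is labelled pre-dose in several places, that 8.1.8 requires the instruction to be given, and that the diary's schedule is only to be followed as closely as possible. That is fair, and sites may well give the instruction verbally. But Section 5.1 makes the diary the vehicle for instructions, and a patient who follows Appendix F literally would dose before the visit.

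**Conclusion.** The point holds in two limited parts.

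For Cohort 1, Appendix F does not agree with Sections 8.1.8 and 9.2. The possible consequence is a mislabelled Day 8 sample that overstates trough by at most about 24% to 63%.

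For Cohort 2, Section 13.4 lacks a rule for end-of-treatment samples. These could hold anything from a full trough to almost nothing: 61% to 80% of a 12-hour trough at 1 day, 9% to 33% at 3 days and 0.2% to 5.8% at 7 days.

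The sizes rest on one-compartment linear kinetics and the stated half-life range; individual values may lie outside it, since Section 2.2 reports a 105% coefficient of variation for clearance. The number of affected samples in either cohort is unknown.

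The documents do not show that the trough summary is contaminated, or that exposure in GBM would be found to be low. Section 2.4 also looks to the surgical cohort, not Cohort 2 plasma, to explain limited activity. The effect is limited to descriptive PK, and PFS6 and its sample size are unaffected.

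**What to change.** 1. Reconcile Appendix F with Sections 8.1.8 and 9.2 so that the patient instruction and the Day 8 pre-dose requirement agree. This costs one diary line.
2. In Section 13.4, state that a sample counts as a steady-state trough only if it is on-treatment, drawn before the next dose, has a recorded time since last dose, and follows no recent hold. Define recent in the plan; five half-lives at the upper end would be 5 × 38 = 190 h, about 8 days. Summarise troughs by the dose being taken, and list end-of-treatment samples separately by time since last dose.
3. Do not add a narrow limit such as 10 to 14 h since the last dose. The morning dose waits for the visit, so an 11AM draw after a 7PM dose is 16 h post-dose: still pre-dose and usable, but outside that limit.

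The cost is one or two sentences and a variable derived from draw and dose times already recorded. The downside is somewhat fewer samples in the trough summary.
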